2.3 Sample Size and Power

The proposed sample size is derived by satisfying the original design assumptions made for the primary efficacy endpoint. It is assumed that the difference in treatment group means is 0 under the null hypothesis (H_0) and is unequal to 0 under the alternative hypothesis (H_1); a 2-sided hypothesis under test. Under the H_1 , the difference in group means of LX9211 minus placebo is expected to be -0.8 units with a common standard deviation (SD) of 1.0 units. These assumptions yield an effect size of 0.8. The effect size is the absolute value of the difference in treatment group means divided by the common SD of that difference. A uniform dropout rate of 0.15 is anticipated, and adjustment of the effect size for this rate results in an estimate 0.68; the adjusted difference in group means is equal to -0.8 units x 0.85 = -0.68. For a 2-sided test sized at $\alpha = 0.05$, 37 patients per treatment group are required under a 1:1 randomization ratio to detect the stated treatment difference under H_1 with statistical power equal to 82.27% under a single stage design. The total planned N = 74 patients.

This study is designed as a group sequential trial with 1 interim look at the 50% information time point and a final analysis at 100%. A non-binding futility boundary will be used to test for futility of the primary endpoint. The futility boundary is 1-

sided with $\alpha = 0.025$ and for the parameters specified, a power estimate of 82.53% is derived.

Sample Size Reestimation

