Analysis and summarization of treatment group comparisons for the safety endpoints will be reported in their original measurement units and converted values to accommodate regulatory review by the Food and Drug Administration and external authorities, where appropriate.

All significance tests will be 2-sided and use a 0.05 α -level unless specified otherwise.

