The change from Baseline to Week 6 in pain interference with sleep based on Question 9F of the ZBPI "Indicate the one number that describes how, in the past 24-hours shingles pain has interfered with your: Sleep (0 [Does not interfere] to 10 [Completely interferes])", rated by patients and collected each evening in the daily pain diary will be summarized using standard descriptive statistics and the treatment effect will be evaluated using a similar MMRM method as specified for the primary efficacy analysis of change from Baseline to Week 6 in ADPS.

In this case, the Baseline value for the interference with sleep using Question 9F of the ZBPI is defined as the value collected at the time of the clinic visit on Day 1. The post-Baseline values will be calculated by week as the mean value of the Question 9F of the ZBPI, rated by patients each evening and collected during the acceptable week period. A minimum of 4 non-missing data within the target week period is required for the calculation.

7.6.2.2 Proportion of patients with $\geq 30\%$ reduction in pain intensity in ADPS based on Question 5 of ZBPI from Baseline to Week 6

Baseline and Week 6 ADPS scores will be based on the same mean values as derived for the primary endpoint. The frequency and percentage of patients with $\geq 30\%$ reduction in pain intensity from Baseline at Week 6 will be presented by treatment group. Response/Non-response categories will be defined as:

- If % change from Baseline $\leq (-30) \rightarrow$ Response
- If missing % change from Baseline or $> (-30) \rightarrow$ Non-response

Where % change from Baseline = $100 * (\text{post-Baseline value} - \text{Baseline value}) / \text{Baseline value}$.

This endpoint will use a CMH test stratified by the different levels of the randomization stratification factors of Baseline severity score (moderate, severe). The treatment group comparisons will be performed at Week 6 only, with descriptive statistics provided for each week. 95% CIs for the difference between 2 proportions will be calculated using the asymptotic Wald method.

7.6.2.3 Proportion of patients with $\geq 50\%$ reduction in pain intensity in ADPS based on Question 5 of ZBPI from Baseline to Week 6

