Baseline and Week 6 ADPS scores will be based on the same mean values as derived for the primary endpoint. The frequency and percentage of patients with $\geq 50\%$ reduction in pain intensity from Baseline at Week 6 will be presented by treatment group. Response/Non-response categories will be defined as:

- If % change from Baseline $\leq (-50) \rightarrow$ Response
- If missing % change from Baseline or $> (-50) \rightarrow$ Non-response

Similarly, this endpoint will be analyzed as for 7.6.2.2.

7.6.2.4 Change from Baseline to Week 6 based on the Questions 9A-G of the ZBPI

The ZBPI is a patient-reported outcome (PRO) assessed on a validated electronic device completed at the time of the clinic visit. The ZBPI, a 9-item questionnaire assesses the severity of pain and its impact on functioning in patients with PHN.

The following pain interference categories based on Questions 9A-G of the ZBPI, completed at the time of the clinic visit, will be analyzed separately:

- General activity
- Mood
- Walking ability
- Normal work
- Relations with other people

- Sleep
- Enjoyment of life

The change from Baseline to Week 6 in pain interference will be summarized using standard descriptive statistics and the treatment effect will be evaluated using a similar MMRM method as specified for the primary efficacy analysis of change from Baseline to Week 6 in ADPS where the time point will be substituted by Visit instead of Week. The Baseline covariate included in the model is the Baseline value of the dependent variable under analysis.

7.6.2.5 Patient Global Impression of Change (PGIC) at Week 6

The PGIC, a 7-point rating scale, will assess the patient's belief about their overall improvement experienced at the end of treatment.

The frequency and percentages of patients within each category at Week 6 will be presented by treatment group. The treatment effect will be evaluated using an ANOVA model with treatment and randomization stratum of Baseline pain severity (moderate, severe) as independent variables. Least-square means of PGIC in each treatment group and the difference between LX9211 and placebo, along with their 95% CIs and p-value will be presented.

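### The responder endpoints pair a severity-stratified CMH test with a plain Wald interval; at 37 per arm coverage is usually about a point low, and test and interval can disagree in borderline results

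*SAP*

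**What the plan says.** SAP 7.6.2.2 covers the proportion with at least a 30% fall in ADPS at Week 6. For the test it says: "This endpoint will use a CMH test stratified by the different levels of the randomization stratification factors of Baseline severity score (moderate, severe"). For the interval it says: "95% CIs for the difference between 2 proportions will be calculated using the asymptotic Wald method". No stratum, weighting or continuity correction is attached to the interval. SAP 7.6.2.3 handles the 50% threshold by reference: "Similarly, this endpoint will be analyzed as for 7.6.2.2".

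Three other statements set the context:
- SAP 7.6.2 counts a missing Week 6 value as non-response, so the denominator stays at about the randomised number, 37 per arm.
- SAP 7.1 fixes the level: "All significance tests will be 2-sided and use a 0.05" α-level.
- SAP 7.6 and Protocol 10.4.2.3 leave the secondary endpoints unadjusted for multiplicity and treat them as exploratory.

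Protocol 10.4.2.2 names the stratified CMH test for these endpoints but no interval.

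**The concern.** The p-value and the interval for the same comparison come from different variance formulas. The CMH test pools the two arms within each severity stratum. As written, the Wald interval estimates each arm's variance separately from crude proportions. In the primary MMRM, the PGIC ANOVA and the NPSI ANCOVA, by contrast, the interval and p-value come from one model that contains the stratum.

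Two things follow. The Wald interval may not reach 95% coverage with arms of 37, particularly at the low rates to which a 50% threshold and non-responder imputation push the data. And a report could show an interval excluding zero beside p > 0.05, or the reverse, with nothing in the SAP to say which one readers should go by. For an exploratory endpoint the estimate and its interval are the main output, so the interval should be sound.

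**Working it through.** **Inputs from the documents.** 37 per arm, 1:1; two-sided 0.05; two severity strata; missing counted as non-response; total N may rise to 148 (Protocol section 6), i.e. 74 per arm. **Assumed, because the documents do not give them:** responder rates and stratum sizes. Unless stated otherwise, strata are 24 moderate and 13 severe per arm.

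**1. The plan's own figure.** SAP 2.3 gives "statistical power equal to 82.27% under a single stage design" for the primary endpoint. With difference 0.68, SD 1 and 37 per arm, the noncentrality is 0.68 × √(37/2) = 2.925. A two-sided t-test on 72 df then has power 82.27%, an exact match. This confirms the arm size; there is no corresponding figure for the responder endpoints.

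**2. Wald coverage.** The interval is d ± 1.96 × √[p₁(1−p₁)/n + p₂(1−p₂)/n]. Enumerating both binomials exactly at n = 37:

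| Assumed rates | Coverage |
|---|---|
| 50% v 30% | 93.8% |
| 25% v 10% | 93.9% |
| 20% v 5% | 93.5% |
| 10% v 2% | 88.1% |
| 60% v 40% | 94.6% |
| 50% v 50% | 95.1% |
| 5% v 5% | 96.1% |

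Over a grid of 10–65% in each arm the mean is 94.2% (range 92.9–95.1%). At 74 per arm the mean is 94.6% (minimum 93.8%), and 10% v 2% rises to 93.7%.

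**3. Is the missing stratum the cause?** No. With equal arms within strata, the Mantel-Haenszel (MH) weights are kₕ/n (kₕ = patients per arm in stratum h), so the weighted difference equals the crude one and only the variance changes. Keeping a Wald variance but adding the strata gave simulated coverage of 93.3–94.2%, no better.

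Ignoring a prognostic stratum widens the interval. Take 60% v 40% in the moderate stratum and 20% v 5% in the severe one:
- Crude rates: (24×0.60 + 13×0.20)/37 = 0.459 and (24×0.40 + 13×0.05)/37 = 0.277.
- Crude SE: √[(0.459×0.541 + 0.277×0.723)/37] = 0.110.
- Within-stratum variances, averaged over strata: (24×0.24 + 13×0.16)/37 = 0.212 and (24×0.24 + 13×0.0475)/37 = 0.172.
- Stratified SE: √[(0.212 + 0.172)/37] = 0.102.

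The crude SE is about 8% too large, and simulated coverage of the plain Wald interval is 96.2%.

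**4. One table, ignoring strata.** With 17/37 v 9/37, d = 0.216 and SE = 0.108, so z = 2.00 and the Wald interval is 0.4 to 42.8 points, which excludes zero. The MH statistic has numerator 17 − 13 = 4 and variance 37²×26×48/(74²×73) = 4.274, so χ² = 16/4.274 = 3.74 and p = 0.053. The tables 12 v 5 (p = 0.055) and 18 v 10 (p = 0.057) behave the same way.

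**5. How often the verdicts at 0.05 differ** (simulated, strata 24/13):

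| Moderate; severe | Wald v CMH | Stratified Newcombe v CMH |
|---|---|---|
| 30 v 30% in both | 0.85% | – |
| 50 v 30% in both | 3.0% | 0.2% |
| 25 v 10% in both | 1.2% | 3.0% |
| 20 v 5% in both | 0.1% | 11.8% |
| 55 v 30%; 35 v 15% | 3.0% (2.69 points Wald-only) | – |
| 60 v 40%; 20 v 5% | 3.4% (3.1 points CMH-only) | 7.9% |
| 70 v 50%; 20 v 5% | 9.0% (nearly all CMH-only) | – |

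Wald-only means that the interval excludes zero while CMH is not significant; CMH-only is the reverse.

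**6. The stratified Miettinen-Nurminen interval.** In one stratum with arm sizes n₁ and n₂, total N and m responders, the MH weight is n₁n₂/N. At a difference of zero, with the N/(N−1) factor, the score variance of the weighted difference is (n₁n₂/N)² × [m(N−m)/N²] × [N/(n₁n₂)] × [N/(N−1)] = n₁n₂m(N−m)/[N²(N−1)]. That is the CMH variance. The numerators also agree, so the interval excludes zero exactly when CMH rejects. Simulation found no disagreement in any scenario tried, with coverage of 94.7–95.5%.

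**The case against.** A stratified CMH p-value beside a crude difference with a Wald interval is a legitimate, fully prespecified choice. The crude difference matches the tabulated percentages, the CMH test is the planned comparison, and no success rule depends on whether this interval excludes zero. The typical shortfall is about 1 point, the 88.1% case needs a placebo rate of 2% (fewer than one expected responder in 37), and some rates show no shortfall. Disagreement is confined to borderline results. All of this stands, and it is why the point is minor.

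A reader might infer that leaving out the stratum makes the interval too narrow. The calculation does not support that: the unpooled variance drives the shortfall, and with a strongly prognostic stratum the interval is too wide. A reader might also take any score-type interval as a cure. Stratified Newcombe is not one: it agrees better with CMH than Wald does at 50% v 30% but much worse at 20% v 5%. The objection does not reach the stratified Miettinen-Nurminen interval, which matches the planned test by construction.

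A larger trial helps only in part. At N = 148 disagreement falls to 0.1–0.5% in most scenarios, but the widening caused by ignoring a strongly prognostic stratum is not a small-sample effect and stays.

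**Conclusion.** The point holds as a minor one. The planned interval and test are built differently, and at 37 per arm the interval usually covers about 1 point less than 95% over plausible rates. The two can contradict each other in roughly 0.1–3% of trials, more (9.0% in the most extreme case tried) if severity is strongly prognostic. The direction depends on how prognostic severity is: mostly Wald-only when it is weak, mostly CMH-only when it is strong. These sizes depend on assumed responder rates and stratum sizes.

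A reader might infer that the trial's main conclusion is at risk. It is not: the primary analysis is the MMRM on ADPS change, and the responder endpoints are secondary, unadjusted and exploratory. Nor do the documents describe the interval as unstratified in so many words; that is the natural reading of a sentence that attaches no strata to it.

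**What to change.** In SAP 7.6.2.2, and so by reference in 7.6.2.3, replace the Wald sentence with one along these lines: *the difference in responder proportions will be estimated as the Mantel-Haenszel-weighted risk difference over the randomised severity strata used in the CMH test, with a stratified Miettinen-Nurminen score 95% confidence interval using the same weights and the N/(N−1) variance factor.* Name both the weights and the factor, because the agreement with CMH depends on them, and have the programmer confirm that the procedure used applies them. Do not list stratified Newcombe as an equivalent.

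The cost is one SAP sentence and a small programming change. Data collection, hypotheses, sample size and the CMH test stay as they are.

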10.4.2.1 Analysis of Primary Efficacy Endpoint

The primary endpoint is the change from Baseline to Week 6 in ADPS. The primary analysis will be based on observed data including data measured after the initiation of rescue medications. Baseline is defined as the average of the Week 2 Run-in period data, provide that ≥ 5 days from that period are available for analysis. The Week 6 mean value will be derived from the 7-day period immediate to the endpoint, provided that ≥ 4 days of non-missing data are collected.

A restricted maximum likelihood-based, mixed-effects model repeated measures (MMRM) approach will be used to assess the difference between LX9211 and placebo in the primary endpoint (ie, change from Baseline to Week 6 in the ADPS derived from data collected daily from Question 5 of the ZBPI instrument). The MMRM model will include fixed effects of treatment, week, treatment-by-week interaction, the randomization stratum of Baseline pain severity, and the Baseline score as covariate. An unstructured covariance structure will be used to model the within-patient error. The Kenward-Roger approximation will be used to estimate the denominator degrees of freedom. Other covariance structures will be explored should convergence not be met. In the event that a rescue medication is used, a supplementary MMRM model will be applied to a dataset that excludes data collected after the initiation of the rescue medication. To assess the robustness of the MMRM analyses performed under the missing at random (MAR) assumption, and given the long half-life of LX9211, pattern mixture models (PMM) with copy reference-based imputation methods will be applied to both datasets (with and

without data collected after the initiation of the rescue medication). The imputed datasets will be combined by use of Rubin's rule and analyzed using an analysis of covariance (ANCOVA) model fitted for the fixed effects of treatment, the randomization stratum of Baseline pain severity, and the continuous fixed covariate of Baseline score.

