10.4.2.2 Analysis of Secondary and Other Efficacy Endpoints

Continuous secondary and other efficacy endpoints: ZBPI scores, PGIC scores and NPSI scores, measured at multiple time points, will be analyzed using a similar modeling strategy as used for the primary endpoint.

Categorical secondary endpoints: The proportion of responders based on Question 5 of ZBPI will be compared between treatment groups using a Cochran-Mantel-Haenszel test stratified by the randomization factor of Baseline pain severity. Patients with missing measurement at Week 6 will be considered non-responders. A nonresponder imputation (NRI) rule will be applied for all analyses based on categorical variables to assign outcomes to missing observations. The percentage of patients who need rescue medication and prematurely dropout will be summarized descriptively. The Kaplan-Meier methods will be used to generate statistical summaries of the time to loss of efficacy variable among patients who achieve $\geq 30\%$ reduction in ADPS based on Question 5 of the ZBPI from Week 6 and Week 11.

The qualitative patient interview substudy will be managed by a vendor (RTI-Health Solutions, Research Triangle Park, NC). The data analysis methods will be detailed in a separate statistical analysis plan and results will be reported separately.

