7.6.1 Primary Efficacy Analysis

The primary endpoint is the change from Baseline to Week 6 in ADPS, based on Question 5 of the ZBPI, the 11-point numerical rating scale (0 [No Pain] to 10 [Pain as bad as you can imagine]). The primary analysis will be based on observed data including data measured after the initiation of rescue medications.

Baseline is defined as the average of the Week 2 Run-in Period data collected by patients in the daily pain diary, provided that ≥ 5 days from that period are available for analysis. The post-Baseline values will be calculated by week as the mean value of the Question 5 for ADPS of the ZBPI, rated by patients each evening and collected during the target week period. A minimum of 4 non-missing data within the target week period is required for the calculation. The change from

Baseline values at post-Baseline weeks will be calculated as the absolute difference between the Baseline value and post-Baseline values, i.e.

$$\text{change from Baseline} = \text{post-Baseline value} - \text{Baseline value}$$

The ADPS calculated for each post-Baseline week until Week 6, and the change from Baseline in ADPS at post-Baseline weeks until Week 6 will be summarized by Week using standard descriptive statistics. Data from all study visits, scheduled and unscheduled, and from the daily pain diary will be listed.

A restricted maximum likelihood-based, MMRM approach will be used to assess the difference between LX9211 and placebo in the primary endpoint (ie, change from Baseline to Week 6 in the ADPS derived from data collected daily from Question 5 of the ZBPI instrument). The MMRM model will include fixed effects of treatment, week, treatment-by-week interaction, the randomization stratum of Baseline pain severity (moderate, severe), and the Baseline ADPS score as a covariate. An unstructured covariance structure will be used to model the within-patient error. The Kenward-Roger approximation will be used to estimate the denominator degrees of freedom. Other covariance structures will be explored should convergence not be met.

The adjusted mean change in ADPS from Baseline to Week 6 for each treatment group and the 95% confidence intervals (CIs) will be estimated in the framework of this model, as well as the between-group differences (comparing LX9211 to placebo) and the 95% CIs for the difference.

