7.6.2 Secondary Efficacy Analysis

Analysis of the secondary efficacy endpoints will be based on the mITT population. Descriptive statistics for all the secondary efficacy endpoints will be presented by treatment group and by study visit/week where appropriate. Data from all study visits, scheduled and unscheduled, and from the daily pain diary will be listed. Post-Baseline data through Week 6 will be used in the analyses where inferential statistics are presented, including observations occurring after discontinuation of

study drug. Figures displaying mean change from Baseline, LS mean change at Week 6, and bar charts displaying proportions, will be presented by treatment group.

Continuous secondary efficacy endpoints: ZBPI scores, measured at multiple time points, will be analyzed using a similar modeling strategy as for the primary endpoint.

The ordinal secondary endpoint, PGIC response at Week 6, will be analyzed using an analysis of variance (ANOVA) model to test and estimate the treatment effect.

Categorical secondary endpoints: the proportion of responders based on the 11-point numerical rating scale (NRS) and the proportion of patients discontinuing study treatment due to lack of efficacy will be compared between treatments using a Cochran-Mantel-Haenszel (CMH) test stratified by the randomization factor of Baseline pain severity (moderate, severe). Patients with missing measurement at Week 6 will be considered non-responders. In general, a non-responder imputation (NRI) rule will be applied to assign outcomes to all study weeks with missing observations.

The Kaplan-Meier (KM) method will be used to generate statistical summaries of the time to loss of efficacy variable among patients who achieve $\geq 30\%$ reduction in ADPS based on Question 5 of the ZBPI from Week 6 to Week 11.

The qualitative patient interview substudy will be managed by a separate vendor (RTI-Health Solutions, Research Triangle Park, NC). The data analysis methods they employ will be detailed in a separate statistical analysis plan and the results will be reported separately by them.

7.6.2.1 Change from Baseline to Week 6 in pain interfering with sleep based on Question 9F of the ZBPI

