In addition to the above planned interim analysis, meetings for an independent DMC data reviews will be scheduled to ensure proper safety assessment during enrollment and study conduct. Initially, proposed timelines for meeting frequency to review unblinded safety data will be based on fractions of patient accrual (eg, 25% and 75% of the original sample size). DMC meetings planned after the interim analysis may be modified in their timing and frequency should the sample size be adjusted upward. A final DMC meeting is planned when the study completes. The DMC will develop a charter and establish criteria for when meetings are to occur, plus identify a time for the planned interim analysis should this latter event fall outside the times of the reoccurring meetings. The DMC review meetings will occur until database lock or at an earlier time deemed suitable by the DMC. This meeting schedule may be modified based on the observed patient accrual rates or signals seen in the safety data. DMC members will also receive unblinded summaries of serious adverse events on a monthly basis to review potential emerging safety trends.

8. Changes in Planned Analysis

For NPSI, an ANCOVA model will be used to evaluate the treatment effect instead of a MMRM since the statistical analysis is conducted for the change scores at Week 6 only.

Since the date and reasons for discontinuation at single-blind Safety Follow-up Period are not collected, the secondary endpoints of the proportion of patients

discontinuing treatment due to lack of efficacy, the time to loss of efficacy from Week 6 to Week 11 defined in [Section 3.2](#) will not be analyzed.

9. Data Issues

Not applicable

10. References

Not applicable

11. Appendices

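### SAP 7.6.2.5 adjusts PGIC at Week 6 for Baseline pain only through the two-level stratum; adding the continuous Baseline ADPS already collected would be a cheap, modest gain in precision, and the departure from the protocol should be recorded in SAP Section 8

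*SAP*

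**What the plan says.** **PGIC in the SAP.** SAP 7.6.2 states: "The ordinal secondary endpoint, PGIC response at Week 6, will be analyzed using an analysis of variance (ANOVA) model". SAP 7.6.2.5 gives the model as an "ANOVA model with treatment and randomization stratum of Baseline pain severity (moderate, severe) as independent variables".

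**PGIC in the protocol.** Protocol 10.4.2.2 lists PGIC among the continuous endpoints: "PGIC scores and NPSI scores, measured at multiple time points, will be analyzed using a similar modeling strategy as used for the primary endpoint". The primary model in protocol 10.4.2.1 contains "the randomization stratum of Baseline pain severity, and the Baseline score as covariate". SAP 7.6.1 makes that specific, with the stratum "and the Baseline ADPS score as a covariate".

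**The SAP's other score endpoints.** Questions 9A-G use a continuous covariate as well as the stratum (SAP 7.6.2.4): "The Baseline covariate included in the model is the Baseline value of the dependent variable under analysis". The NPSI ANCOVA (SAP 7.6.5.1) also has stratum and continuous Baseline score. Sleep interference (7.6.2.1) and clinic-visit Question 5 (7.6.5.2) take over the primary model by reference.

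**Declared changes.** SAP Section 8 says: "For NPSI, an ANCOVA model will be used to evaluate the treatment effect instead of a MMRM". The reason given is that NPSI change scores are analysed at Week 6 only. PGIC is not mentioned there.

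**The concern.** Among the score endpoints, PGIC alone has no continuous Baseline term, and no reason is given. The stratum is a coarse summary of Baseline pain: SAP 7.2 forms it from the rounded 14-day run-in mean, with 5-7 as moderate and 8-9 as severe, so any mean from 4.5 up to just under 7.5 falls in one level. If Baseline pain predicts PGIC within a stratum, two things follow. Residual variance that a covariate could remove stays in the error term. A chance difference in Baseline pain between arms within strata also carries into the PGIC contrast, in proportion to the within-stratum slope.

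A smaller issue is record-keeping. The reason Section 8 gives for leaving the MMRM for NPSI applies equally to PGIC, because both have scheduled post-Baseline assessments only at Weeks 6 and 11. One change is recorded and its parallel is not.

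**Working it through.** **The plan's own figure.** No power or precision figure is given for PGIC. The primary endpoint's figure reproduces: with 37 per group, difference 0.68, SD 1.0 and 2-sided 0.05 (SAP 2.3), the noncentral t with 72 df and noncentrality 0.68/√(2/37) gives 82.27%, as stated. The total of 74 is used below.

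**Is the covariate available?** Randomization requires at least 70% of diary entries in run-in Week 2: 0.70 × 7 = 4.9, so 5 days. The Baseline ADPS rule (SAP 6.1.1) also requires at least 5 days. Patients randomized per protocol should therefore have a value, apart from any small mismatch when Day 1 uses its +3-day window.

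**Net change in interval width.** Let r be the correlation of Baseline ADPS with PGIC within stratum and arm. The documents do not give it, so r = 0.1, 0.2 and 0.3 are assumptions. Three factors apply when one covariate is added to the planned ANOVA at n = 74:

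1. Residual SD: √(1 - r²) = 0.9950, 0.9798, 0.9539.
2. Cost of estimating the extra slope. The expected variance inflation for p covariates is 1 + p/(n - p - 3). Going from p = 1 (stratum) to p = 2 gives (1 + 2/69)/(1 + 1/70) = 1.0145, with square root 1.0072.
3. t quantile with 70 rather than 71 df: 1.9944/1.9939 = 1.0002.

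The cost factor is 1.0072 × 1.0002 = 1.0075.

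| Within-stratum r | Before cost | Net of cost |
|---|---|---|
| 0.1 | -0.5% | +0.2% |
| 0.2 | -2.0% | -1.3% |
| 0.3 | -4.6% | -3.9% |

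Break-even is where √(1 - r²) = 1/1.0075, that is r of about 0.12. With about 63 evaluable patients (74 × 0.85), the result at r = 0.1 is +0.4%.

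**How much does the stratum already do?** This needs a Baseline distribution, which the documents do not give. Assumed mean/SD values of 6.0/1.0, 6.5/1.2 and 7.0/1.2 were simulated through the SAP's cut. The correlation c between Baseline ADPS and the stratum came out at 0.56 to 0.76, so the stratum carries c² = 31% to 58% of the Baseline pain information. The SD of a chance arm difference in Baseline ADPS is √(4/74) = 0.23 SD without stratification and √(4(1 - c²)/74) = 0.15 to 0.19 SD with it.

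Expressed through the overall correlation of Baseline ADPS with PGIC, and net of cost, the interval changes by +0.4% to +0.5% at 0.1, -0.1% to -0.7% at 0.2, -1.3% to -2.5% at 0.3 and -5.6% to -9.1% at 0.5. These differ from the table only because part of an overall correlation is already absorbed by the stratum.

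**The case against.** The strongest defence is that the ANOVA is a fair reading of the protocol. PGIC asks about change since the start of the study, so it has no Baseline value. Up to Week 6 it has one scheduled assessment, so the repeated-measures model cannot be fitted as such. Remove from the primary model the week terms and the outcome's own Baseline, and treatment plus stratum remains, which is exactly the SAP's model. For Questions 9A-G the SAP's covariate is the endpoint's own Baseline, not ADPS. The model is also stated openly in SAP 7.6.2 and 7.6.2.5.

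Most of this stands. The protocol does not name Baseline ADPS as the PGIC covariate, so adding it is an improvement and not the restoration of a prescribed model. It does not follow that nothing is left to gain. A covariate need not be the outcome's own Baseline, and the planned model already adjusts PGIC for Baseline pain, only in dichotomised form. The undeclared change of model remains whichever covariates are preferred.

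A reader might also infer that PGIC is not adjusted for Baseline pain at all, or that the comparison is biased. The documents support neither. The severity stratum is in the model and is a randomization factor (protocol 6.6), and under randomization the ANOVA contrast is unbiased.

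**Conclusion.** The point holds as a cheap improvement. The PGIC model uses Baseline pain only as a two-level factor and leaves out a continuous measure available for essentially every randomized patient. What is forgone is some precision and some protection against within-stratum chance imbalance; validity is not affected. Secondary endpoints are exploratory and unadjusted for multiplicity (SAP 7.6), so the primary conclusion does not depend on this.

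The size rests on a within-stratum correlation that the documents do not give. At 74 patients the net effect on interval width is about +0.2%, -1.3% and -3.9% for 0.1, 0.2 and 0.3. It would be tempting to call the precision free, but below a correlation of about 0.12 the covariate costs slightly more than it returns. The missing Section 8 entry depends on no assumption.

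**What to change.** In SAP 7.6.2.5, replace the ANOVA by an ANCOVA with treatment, randomization stratum and continuous Baseline ADPS, and align the sentence in SAP 7.6.2. In SAP Section 8, record that PGIC is analysed by a single-time-point model at Week 6 instead of the primary endpoint's modelling strategy, as is done for NPSI, and name the covariate chosen. If the sponsor prefers to keep the ANOVA, the Section 8 entry and a one-line reason are still needed.

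The cost is one model term, 1 degree of freedom and a few sentences. No new data are needed, and the contrast still estimates the difference in mean PGIC. A patient without a Baseline ADPS would drop out of the ANCOVA, which should be rare given the matching diary rules. The change should be made before unblinding.
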